Full study protocol and Statistical analysis plan

Department of Dermatology, St. Vincent's Hospital, College of Medicine, The Catholic University of Korea

NCT03933774

January 2, 2020

Study protocol: Adult patients aged ≥ 19 years with stable, non-segmental vitiligo symmetrically distributed over the face are enrolled. The stable vitiligo is defined as follows: the absence of progression for at least 6 months prior to enrollment, and the absence of Koebner's phenomenon, trichromic lesion, or confetti-like depigmentation. The exclusion criteria are pregnancy, sensitive skin, or photosensitivity. Each side of the face will be randomly assigned to receive the topical tretinoin 0.05% (w/v) cream (tretinoin group) or moisturizer (control group) every night during the period of NBUVB phototherapy, which will be performed on the entire face twice weekly for 12 weeks. The initial dose is 100 mJ/cm² and is increased by 50 mJ/cm² at each subsequent session until a pink erythema that does not persist for ≥24 h appear. Patients who complained of erythema or irritation are instructed to mix topical tretinoin with moisturizer in proportions to relieved their complaints.

The primary outcome is the degree of hyperpigmentation (the change in the L*value [delta L*]) of the darkest spots on either side of the face, using a spectrophotometer at baseline and every month thereafter. The secondary outcome is the treatment response to phototherapy assessed by deriving the VESTA by reference value based on clinical photographs obtained at baseline and every month thereafter. All adverse events are recorded at each visit.

Statistical analysis plan: The paired t-test will be used to compare the delta L*values of the two groups. The treatment response proportions will be compared using the McNemar test. All statistical analyses will be performed using R ver. 3.6.1 software (R Foundation for Statistical Computing, Vienna, Austria).

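### No left/right balancing of the tretinoin side is described and the paired t-test has no side term, so any consistent left-right difference in delta L\* costs precision (minor, optional improvement)

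*Combined protocol and SAP*

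**What the plan says.** The Study protocol paragraph gives the allocation in one clause: "Each side of the face will be randomly assigned to receive the topical tretinoin 0.05% (w/v) cream (tretinoin group) or moisturizer (control group". No randomisation method, blocking, or left/right balance across patients is stated.

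The primary outcome is "the change in the L*value [delta L*]) of the darkest spots on either side of the face", measured at baseline and monthly. The Statistical analysis plan paragraph gives the primary analysis in one sentence: "The paired t-test will be used to compare the delta L*values of the two groups". Side is not mentioned there, nor in the McNemar comparison for the secondary outcome.

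Two other statements bear on how far left and right might differ. Patients with "stable, non-segmental vitiligo symmetrically distributed over the face are enrolled", and the phototherapy is one "which will be performed on the entire face twice weekly for 12 weeks". The documents state no sample size, significance level, power or SD.

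**The concern.** With one side of each face on tretinoin and the other on moisturizer, what is randomised is the patient, to tretinoin-left or tretinoin-right. Left and right then play the part that the two periods play in a crossover. Pairing removes what the two sides share. It does not remove a consistent left-right difference in how much L\* changes over the 12 weeks.

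Such a difference enters a patient's tretinoin-minus-control value with a plus sign if tretinoin was on one side and a minus sign if it was on the other. The planned test counts it as noise, although the design records exactly which sign applies. Two things are at stake:

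- power is lost to a nuisance effect that could be estimated and removed;
- in the one trial that is run, the estimate moves if more patients have tretinoin on one side than the other.

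**Working it through.** The plan has no power or sample-size figure to reproduce, so the check is algebra plus simulation under stated assumptions.

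**Inputs from the documents.** One side per patient on each cream, allocation random with no restriction described, outcome delta L\*, paired t-test with no side term.

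**Assumed inputs.** N = 20 patients (16, 30 and 40 as variants); two-sided 5% level; residual SD of the within-patient difference = 1; treatment effect τ set to give 80% power when there is no side effect (τ = 0.66 SD at N = 20); λ, the left-minus-right difference in delta L\*, between 0 and 0.5 SD.

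**Model.** For patient i, d_i = τ + s_i λ + e_i, where s_i = +1 if tretinoin is on the left and −1 if on the right.

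**Step 1: precision over simple randomisation.** Var(mean d) = (1 + λ²)/N. The multiplier is 1 + 0.25² = 1.06 at λ = 0.25 and 1 + 0.5² = 1.25 at λ = 0.5. In simulation the planned test kept its 5% level and had no average bias.

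**Step 2: shift given the realised split.** With k of N patients having s = +1, the estimate moves by λ(2k/N − 1).
- At N = 20, a 13:7 split or worse has probability 0.263 (exact binomial). At 13:7 the shift is λ × (26/20 − 1) = 0.30λ.
- At λ = 0.25 that is 0.075 SD, or 0.075/0.66 = 11% of the assumed effect. At λ = 0.5 it is 0.15 SD, or 0.15/0.66 = 23%.

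**Step 3: power at N = 20 (simulation).**

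| λ (SD) | Paired t, unrestricted | Paired t, balanced | Side term, unrestricted | Side term, balanced |
|---|---|---|---|---|
| 0 | 0.80 | 0.80 | 0.775 | 0.798 |
| 0.25 | 0.775 | 0.78 | 0.775 | 0.80 |
| 0.5 | 0.71 | 0.72 | 0.775 | 0.80 |

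**Step 4: balance without the side term.** The true variance is then 1/N, but the t-test still estimates about (1 + λ²)/N. At λ = 0.5 the standard error is about √1.25 = 1.12 times too large and the actual type I error is 0.029. Balancing alone therefore recovers little of the lost power.

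**Step 5: side term without balance.** The adjusted estimate has variance (1/4)(1/k + 1/(N − k)), which is 1/N only when k = N/2. At 13:7 it is 0.25 × (1/13 + 1/7) = 0.0549, against 1/20 = 0.05. When λ = 0, the loss against the plain paired t-test is about 3 points at N = 16, 2.5 at N = 20, 1.6 at N = 30 and 1.1 at N = 40. At N = 20 the two analyses break even near λ = 0.25.

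**The case against.** The strongest reply is that the planned analysis is a standard one and is not wrong. That stands. A reader might infer from the shift in an uneven split that the paired t-test is biased or invalid. It is neither: under unrestricted randomisation its variance already covers chance imbalance, and its level and average estimate are correct.

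The second reply is that λ has no support in the documents, and what they do say suggests that it may be small. Lesions must be symmetric, phototherapy covers the whole face, and a constant left-right difference in L\* cancels in the change from baseline. Only a difference in the change, in the same direction across patients, matters. This also stands, though it does not settle the matter. The symmetry criterion concerns where the vitiligo lies, while the outcome is darkening of the darkest spots, and no data on left-right differences are given. At λ = 0.25 the loss is only 2 to 3 points. The larger loss needs λ = 0.5, about three quarters of the assumed effect (0.5/0.66 = 0.76).

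Two other inferences are tempting. The words "Each side of the face will be randomly assigned" might suggest that both sides of one face could draw the same cream. The paired t-test and the McNemar test each need one side of each kind per patient, so the plan does not support that reading. Nor does silence on blocking show that balance was absent. In so short a document it shows only that balancing is not described.

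**Conclusion.** The point holds as a minor, optional improvement. The plan neither describes left/right balancing nor uses side in the primary test. Any consistent left-right difference in delta L\* therefore remains in the error, and a chance uneven split shifts the observed estimate.

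Under the assumptions of 20 patients and an effect set for 80% power, doing both (balance and side term) would gain 2 to 3 points of power at λ = 0.25 SD and about 9 points at λ = 0.5 SD. Both λ and N are assumed. If left and right behave alike, there is nothing to gain.

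**What to change.** State that each patient is randomised, in permuted blocks, to tretinoin left and moisturizer right or the reverse. Analyse the within-patient tretinoin-minus-control difference in delta L\* with an intercept (the treatment effect) and a +1/−1 term for the side that received tretinoin, on N − 2 degrees of freedom. This takes one sentence in the allocation procedure and one model term. It uses one degree of freedom, worth about 0.2 points of power at N = 20 if λ is zero.

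If allocation is already fixed, the choice depends on how it was done:

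- **Unrestricted:** keep the paired t-test as primary and report the side-adjusted model as a prespecified sensitivity analysis. As a primary analysis the side term would cost about 1 to 3 points of power when λ is zero.
- **Blocked by side in practice:** say so, and include the side term in the primary model, since without it the test is conservative whenever λ is not zero.

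### Does measuring hyperpigmentation by delta L* alone, without a redness reading, undermine the primary comparison?

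*Combined protocol and SAP*

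**What the plan says.** The Study protocol section of the combined protocol and SAP defines the primary endpoint in these words: "The primary outcome is the degree of hyperpigmentation (the change in the L*value [delta L" (the asterisk and closing bracket follow). It is taken on the darkest spots of each side, "using a spectrophotometer at baseline and every month thereafter". No second colour coordinate is named, and no interval is set between a reading and the last irradiation or cream application.

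The design is split-face. Each side is randomised to tretinoin cream "or moisturizer (control group) every night during the period of NBUVB phototherapy". Phototherapy is common to both sides: "which will be performed on the entire face twice weekly for 12 weeks".

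Four statements bear on redness:

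- The phototherapy dose is raised "at each subsequent session until a pink erythema that does not persist for ≥24 h appear".
- "The exclusion criteria are pregnancy, sensitive skin, or photosensitivity".
- "Patients who complained of erythema or irritation are instructed to mix topical tretinoin with moisturizer in proportions to relieved their complaints".
- "All adverse events are recorded at each visit".

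The Statistical analysis plan section compares delta L* between the sides by a paired t-test. Neither section gives a redness rate, a standard deviation, a target difference or a sample size.

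**The concern.** L* is overall lightness. If reddened skin reads darker, a red tretinoin side would score as more pigmented than it is. Pairing removes what the two sides share, but not redness that follows the allocated cream. Subtracting baseline does not help, because baseline precedes treatment. More patients would not help either, since the shift is systematic.

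The protocol's own dilution instruction shows that irritation was expected. Dilution depends on a complaint, and adverse events are not said to be recorded by side.

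At stake would be a masked benefit of tretinoin, or an apparent darkening on its side. A reading time missed at the visit cannot be recovered later. Setting a time and storing a redness coordinate (a*) would cost little: one baseline plus 3 four-weekly readings in 12 weeks, on 2 sides, is (1 + 3) × 2 = 8 values per patient per spot.

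**Working it through.** The plan states no figure that could be reproduced here. The check therefore asks what a bias would require, how large it could be, and whether the two conceivable changes would deal with it. Every number in steps 2 to 5 rests on assumed inputs.

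**1. What the bias requires.** Let redness lower an L* reading by k. Let p_T and p_C be the shares of tretinoin and control sides that are red at a reading. With no treatment redness at baseline, the mean side difference in delta L* is

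true pigment difference − k × (p_T − p_C).

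Phototherapy redness that is equal on both sides adds the same amount to p_T and p_C and drops out. A bias needs both k > 0 and p_T > p_C at the reading. The documents state neither. They show that intolerance was foreseen and is met by dilution, not that excess redness remains at the monthly visit.

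**2. Possible size.** Assume an excess p_T − p_C of 0 to 40 percentage points and k of 0.5 to 3 units.

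- Lowest: 0 × k = 0.
- Middle: 0.20 × 2 = 0.4 units.
- Highest: 0.40 × 3 = 1.2 units.

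**3. Effect on the test.** Express the shift as r, in standard deviations of the paired differences, at a two-sided 5% level with 20 pairs. With no true pigment difference, the paired t-test rejects in 5%, 7%, 19% and 57% of trials at r = 0, 0.1, 0.25 and 0.5. Against a true effect of 0.6 SD that redness opposes, power is 72%, 56%, 32% and 6%. The effect therefore runs from none to material, and the documents do not locate the trial on that scale.

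**4. Would a fixed reading time help?** Reading just before irradiation limits fresh phototherapy redness. By step 1, the part shared by both sides already cancels. The part said not to cancel comes from the nightly cream, and a time set against irradiation does not remove it. Nothing in the protocol suggests that the two sides are read in different sessions.

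**5. Would reporting a* help?** A simulation of 4,000 trials per setting assumed 30 pairs, a paired SD of delta L* of 3, a true side difference of 1.5, 20% of control sides red, a* up by 3 when red, and a* noise of SD 1 on each of four readings. The L* bias column uses k = 2, so it equals excess × 2.

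| Excess redness (points) | L* bias | Mean delta a* difference | 95% CI half-width | CI above zero |
|---|---|---|---|---|
| 0 | 0 | 0.0 | 0.97 | 3% |
| 10 | 0.2 | 0.3 | 1.00 | 9% |
| 20 | 0.4 | 0.6 | 1.03 | 21% |
| 40 | 0.8 | 1.2 | 1.02 | 63% |

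The 20-point row can be checked by hand, treating the sides as independent:

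- Variance = 9 × (0.2 × 0.8 + 0.4 × 0.6) + 4 × 1 = 3.6 + 4 = 7.6.
- Standard error = √(7.6 / 30) = 0.503.
- Half-width = 2.045 × 0.503 = 1.03, as simulated.

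Pigment may itself move a*. If it does so by −0.2 or −0.4 per L* unit, a true difference of 1.5 moves the a* difference by −0.2 × 1.5 = −0.3 or −0.4 × 1.5 = −0.6. Against the redness signals of +0.3 (10 points) and +0.6 (20 points), the sum is zero in each case. The L* bias of 0.2 or 0.4 is still there. A near-zero a* difference could then reassure falsely.

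**The case for a change.** The strongest argument for the concern is that its factual basis is correct. Delta L* is the only stated measure of hyperpigmentation. The other efficacy outcome, VESTA, concerns response to phototherapy and is no check on it. The cream is one-sided, irritation is anticipated, and the four safeguards reduce excess redness without excluding it. The 24-hour limit concerns phototherapy erythema, not irritation from the cream. A plan silent on redness leaves a reader unable to say whether a shift of zero or of 0.25 SD applied, and recording a* is cheap.

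What stands is the general limitation: one lightness value cannot apportion a change between pigment and redness. A team that stores a* as description does no harm.

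What does not stand is the step from that limitation to a fault in this plan. The mechanism and its size come wholly from assumptions. Even if redness does lower L*, it works against tretinoin and would not create a false benefit. Reporting a* would leave the endpoint, the test and the included readings as they are, with no adjustment and no decision rule. Adjusting for a* is no way out: with no excess redness at all, and the pigment shifts used above, the regression-adjusted estimate falls from 1.5 to 1.35 or 1.11.

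**Conclusion.** The concern does not hold as an error in the plan. Delta L* compared by a paired t-test is a coherent primary analysis for a split-face design, and the documents contain no figure, rule or statement that contradicts it.

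The possible bias is of unknown size and may be zero. The range of 0 to 1.2 L* units depends on assumed redness rates, on an assumed drop in L* when skin is red, and on excess redness remaining at the reading despite the exclusions and dilution. None of these is in the documents.

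The changes that suggest themselves would neither remove the bias nor reliably detect it, and they would alter no result. That a spectrophotometer outputs a* together with L* is itself an assumption. Whether to store a* is a choice of descriptive data, and no amendment is needed on this point.

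### A possible refinement: the paired t-test on delta L* is valid, but it fixes the slope on the baseline side difference at 1; a prespecified regression would estimate that slope from data already collected

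*Combined protocol and SAP*

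**What the plan says.** The statistical analysis plan gives one sentence for the primary comparison: "The paired t-test will be used to compare the delta L*values of the two groups". It mentions no baseline covariate or regression.

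The study protocol defines the outcome as "the degree of hyperpigmentation (the change in the L*value [delta L*]) of the darkest spots on either side of the face", measured "using a spectrophotometer at baseline and every month thereafter". Baseline L* is therefore available on both sides of every face.

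Allocation is within patient: "Each side of the face will be randomly assigned" to tretinoin or moisturizer. Eligibility asks for "stable, non-segmental vitiligo symmetrically distributed over the face", but sets no limit on how far the darkest spots of the two sides may differ in L*.

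The documents give no sample size, SD, correlation or significance level, and do not say which monthly visit is tested.

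**The concern.** A paired t-test on change scores is a regression in which the coefficient of the baseline side difference has been set to 1 in advance. That is the best choice only if the side difference seen at baseline carries over to follow-up in full, on average.

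If it carries over only in part (b below 1), subtracting all of it over-corrects a chance imbalance, and the error has the opposite sign to the imbalance. If side differences widen during treatment so that b exceeds 1, subtracting it once under-corrects.

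What is at stake is the reading of one particular trial in which the sides happened to start at different mean L*. Readers of a split-face trial will ask whether such a difference drove the result. An adjustment first chosen after the data are seen is less convincing than one written down beforehand.

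**Working it through.** **Inputs from the documents.** Outcome: delta L* per side, taken here as follow-up minus baseline. Test: paired t-test. Sides randomised within patient, so the expected baseline side difference is zero. There is no stated figure to reproduce.

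**Assumed inputs.** Number of pairs n; correlation r between the baseline and follow-up side differences; ratio k of their SDs (follow-up/baseline); two-sided 5% level.

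**Model.** Let D0 and D1 be the tretinoin-minus-control differences in L* at baseline and at the tested visit, with D1 = τ + b·D0 + e and b = r·k. The within-patient difference in delta L* is D1 − D0.

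**Step 1: conditional error.** The paired test estimates mean(D1 − D0) = τ + (b − 1)·mean(D0) + mean(e). Given the observed imbalance, it is off by (b − 1)·mean(D0). Averaged over randomisation, mean(D0) is zero and the error vanishes. The regression intercept at D0 = 0 does not carry this term.

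Example with n = 25, k = 1 and an imbalance of 2 standard errors, i.e. 2/√25 = 0.4 SD of D0. The standard error of the change estimate is √(2(1 − r)/25).

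| r (= b) | Error, SD of D0 | SE of change estimate | Error in SEs |
|---|---|---|---|
| 0.5 | −0.5 × 0.4 = −0.20 | 0.200 | −1.00 |
| 0.7 | −0.3 × 0.4 = −0.12 | 0.155 | −0.77 |
| 0.9 | −0.1 × 0.4 = −0.04 | 0.089 | −0.45 |

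**Step 2: false-positive rate of the paired test, given the imbalance** (n = 25, k = 1, noncentral t).

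| r | Imbalance 0 | 1 SE | 2 SE |
|---|---|---|---|
| 0.5 | 2.5% | 4.9% | 12.8% |
| 0.7 | 3.5% | 5.0% | 9.7% |
| 0.9 | 4.5% | 5.0% | 6.6% |

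An imbalance of 2 SE or more arises in about 5% of trials. Over all randomisations, the simulated rate of the paired test was 4.9–5.2% in every setting tried with n = 10, 20 or 30. The regression holds 5% at each imbalance if errors are linear in D0, normal and of constant variance.

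**Step 3: precision.** Variance ratio, regression to paired test:

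k²(1 − r²) / [(1 − rk)² + k²(1 − r²)] × (n − 2)/(n − 3)

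With k = 1 this is (1 + r)/2 × (n − 2)/(n − 3). For n = 25 and r = 0.5: 0.75 × 23/22 = 0.78.

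| n | r = 0.5 | r = 0.7 | r = 0.9 | Largest average loss, 1/(n − 3) |
|---|---|---|---|---|
| 10 | 0.86 | 0.97 | 1.09 | 14% |
| 15 | 0.81 | 0.92 | 1.03 | 8% |
| 25 | 0.78 | 0.89 | 0.99 | 4.5% |

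The largest loss is reached at b = 1. Unequal variances change the picture: with k = 1.5 and n = 25, r = 0.5, 0.7, 0.8, 0.9 give b = 0.75, 1.05, 1.20, 1.35 and ratios 1.01, 1.04, 1.00, 0.81.

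**Step 4: simulation check** (n = 20, 40,000 trials per setting). In the tenth of trials with the largest positive imbalance (mean about 0.39 SD), the change estimate was off by −0.19 SD at b = 0.5, 0.00 at b = 1 and +0.08 SD at b = 1.2. The regression was off by at most 0.006 SD in those three settings. For an effect of 0.5 SD, power was 56% (paired) against 66% (regression) at b = 0.5, and 80.5% against 78.2% at b = 1.

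**Step 5: choice of outcome and centring.** Using D1 − D0 or D1 as the outcome gives the same intercept and the same t-statistic, so delta L* can stay. Centring D0 at its sample mean must be avoided. With delta L* as outcome, it returns the paired-test estimate with too small a standard error: the overall false-positive rate at n = 25 is 8.6% at r = 0.5, falling to 5.6% at r = 0.9. With follow-up L* as outcome, the rate is 8.6% rising to 37.7%.

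**The case against.** The strongest objection is that this is a preference. Randomising sides and applying a paired test to baseline-subtracted values is coherent, unbiased over randomisation, and keeps its 5% level overall. At n = 25 the conditional rate is at or below 5% for imbalances up to about 1 SE, and the imbalances that matter are uncommon. All of that stands, and it is why the point is no more than an optional improvement.

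It also stands that every magnitude depends on an assumed n, r and k. With few pairs and b near 1 the regression loses a little: at n = 10 and b = 1, simulated power for a 0.5 SD effect fell from 47% to 42%.

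The regression is easier to misapply than the paired test, as the centring figures show, and its conditional 5% level needs model assumptions. When the residual spread grew with the size of the baseline side difference, its simulated rate at imbalances of 2 SE or more was about 1–4% for n = 10 to 25, which is conservative rather than unsafe.

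The lack of an L* limit in the symmetry criterion adds little, since chance imbalance can arise in any randomised trial.

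None of this removes the case for the change. It is specific, uses a reading the trial already takes, and has a bounded cost.

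**Conclusion.** The point holds as a cheap improvement. The planned test fixes the slope at 1 and is off by (b − 1) times any chance baseline imbalance; a prespecified regression removes that conditional error.

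Under assumed equal variances, the average variance falls by about 22% at r = 0.5 and 11% at r = 0.7 with 25 pairs, and hardly changes at r = 0.9. With 10 pairs and r = 0.9 it rises by 9%. Which case applies cannot be settled from the documents.

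A reader might infer that the paired t-test is biased, that it ignores baseline, or that adjustment is sure to add power. The documents support none of these. Sides are randomised, delta L* already subtracts baseline, and no n, r or SD ratio is given from which a gain could be shown.

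**What to change.** Add to the statistical analysis plan, before the data are seen:

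> At each visit where the paired t-test would be applied, the within-patient difference in delta L* (tretinoin minus control) will be regressed on the within-patient difference in baseline L* (tretinoin minus control), entered without centring. The intercept, with its 95% confidence interval and p-value, is the primary result. The paired t-test on delta L* is a prespecified sensitivity analysis.

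State explicitly that the covariate is not to be centred at its sample mean. The primary outcome is unchanged, and no new measurement or software is needed. Which monthly visit is primary still has to be named, whichever test is used.

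**Cost.** The planned paired t-test moves from primary to sensitivity analysis. The regression uses one degree of freedom and carries an average variance loss of at most 1/(n − 3), reached when b = 1: 14% at 10 pairs, 8% at 15, 4.5% at 25. Linearity and constant spread of the residuals should be checked.

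### The only primary analysis is a paired t-test, with no tested month, analysis set, post-stopping measurement or missing-data rule; run at week 12 on observed pairs, it omits patients without that reading and leaves their earlier monthly readings unused

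*Combined protocol and SAP*

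**What the plan says.** The document is a single combined protocol and SAP.

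- **Treatment.** In the study protocol paragraph, one side of the face receives tretinoin and the other moisturizer, "every night during the period of NBUVB phototherapy". The phototherapy is a course "which will be performed on the entire face twice weekly for 12 weeks". The cream therefore depends on the phototherapy; nothing makes the phototherapy depend on the cream.
- **Tolerability.** The one instruction is "Patients who complained of erythema or irritation are instructed to mix topical tretinoin with moisturizer". There is no rule for stopping treatment, and no statement on whether a patient who stops is still measured.
- **Primary outcome.** "The primary outcome is the degree of hyperpigmentation (the change in the L*value [delta L*]) of the darkest spots on either side of the face", measured "using a spectrophotometer at baseline and every month thereafter". No month is singled out.
- **Primary analysis.** The statistical analysis plan paragraph says "The paired t-test will be used to compare the delta L*values of the two groups". It adds the McNemar test for the response proportions and the software. It defines no analysis set and says nothing about missing readings.

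**The concern.** Each patient is a matched pair, and a paired t-test takes one difference per patient. A patient whose pair is missing at the tested time contributes nothing, and several months cannot be combined. The natural tested time is the end of the 12-week course. The default is then a complete-pair analysis at week 12, in which someone who attended month 1 or 2 and then left is treated as if never observed.

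Randomising sides does not protect against this. Pairing removes differences between patients, but it does not stop whole patients being lost because of how one side reacted. The protocol anticipates irritation and its remedy acts on the tretinoin side, so loss related to one treatment is plausible. The estimate would then describe patients who stayed, not all who were randomised. Because the plan is silent, whether such patients are measured and counted could also be settled after the data are seen.

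**Working it through.** **What can be reproduced.** Nothing numerical: the documents give no alpha, power, effect size, SD, sample size or dropout rate. Every input below is an assumption, and sizes are in SDs of the within-patient side difference in delta L*. Monthly visits are taken to fall so that the third is the week-12 reading.

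**Step 1: bias of the observed-pair mean, direct form.** Let p be the fraction without a week-12 reading, and k the gap in mean side difference between those who stay and those who leave. The observed-pair mean is off by p × k.

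| p | k = 0 | k = 0.5 SD | k = 1 SD |
|---|---|---|---|
| 10% | 0 | 0.05 | 0.10 |
| 20% | 0 | 0.10 | 0.20 |
| 30% | 0 | 0.15 | 0.30 |

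**Step 2: the same bias through the month-1 reading.** Assume side differences at month 1 and week 12 correlate 0.6, and that patients leave after month 1 when a trait, correlated r with the month-1 side difference, is in its top fraction p. Then

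bias = 0.6 × r × φ(z) / (1 − p), with z = Φ⁻¹(1 − p).

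- p = 0.10: z = 1.2816, φ(z) = 0.1755, and 0.1755 / 0.90 = 0.195. Bias = 0.6 × r × 0.195.
- p = 0.20: z = 0.8416, φ(z) = 0.280, and 0.280 / 0.80 = 0.350. Bias = 0.6 × r × 0.350.

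| p | r = 0.3 | r = 0.5 | r = 1 |
|---|---|---|---|
| 10% | 0.035 | 0.058 | 0.117 |
| 20% | 0.063 | 0.105 | 0.210 |

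**Step 3: does using the month-1 reading help?** Simulation with an assumed 40 patients (4000 runs; r = 0.5 and 1) confirmed the observed-pair biases. An estimate that also uses the leavers' month-1 difference had bias below 0.01 SD. Its standard error was 0.17 to 0.19, against 0.16 to 0.18 for observed pairs. This set-up favours the method, because leaving relates to the week-12 result only through the observed month-1 reading.

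**Step 4: a less favourable case.** Let leaving also depend on the part of the week-12 difference that month 1 does not predict (assumed loading 0.5, with r = 0.5; 40 patients, 8000 runs). The observed-pair bias is about 0.13 SD at 10% and 0.24 SD at 20%; the estimate using month 1 is still off by about 0.08 and 0.15 SD. With r = 0 there is no reduction at all.

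**Step 5: precision.** If full enrolment gave 80% power at an assumed two-sided alpha of 0.05, losing 10%, 20% or 30% of pairs leaves about 75%, 70% and 63% with 20 patients, and about 76%, 70% and 64% with 40.

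**The case against.** The strongest reply is that the plan does not exclude anyone. A reader might infer that patients who stop early necessarily fall out of the primary result, or that intolerance on the tretinoin side removes both sides. The text supports neither inference:

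- The monthly readings are not conditional on treatment. A patient who stops but is still measured stays in the paired test.
- The cream is tied to the phototherapy, not the reverse. A patient who stops tretinoin could continue phototherapy and measurement. Losing both sides needs the further step that the patient leaves the study or misses the reading.
- No tested month is named. If an earlier month or the last available reading were used, leavers with the reading concerned would be kept.
- Stopping for erythema is not described. Transient erythema is the endpoint of dose titration, complaints are met by diluting the tretinoin, and sensitive skin and photosensitivity are exclusions. All of this works against stopping, and no dropout rate is given.

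All four points stand, and they make the concern conditional. They do not remove it: nothing in the document says that stopped patients are measured, which reading is tested or what happens when it is missing. It is also fair to object that the near-zero bias of the modelled estimate in Step 3 follows from its assumptions; Step 4 shows the limit.

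**Conclusion.** The gap is real, and it is one of omission. With a paired t-test as the only primary analysis and the handling of missing readings left open, a week-12 test on observed pairs drops patients without that reading and wastes what was already measured on them. The resulting bias is zero if leaving is unrelated to the tretinoin side's reaction. Otherwise its size and direction are unknown. Under the Step 2 assumptions it is roughly 0.04 to 0.12 SD at 10% leaving and 0.06 to 0.21 SD at 20%. These figures show scale only and do not describe this trial. The plan should be changed because the remedy is inexpensive and touches the primary result, not because serious bias has been shown.

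**What to change.** 1. Name week 12 as the primary time point and state which monthly visit supplies it.
2. State that a patient who stops the cream or the phototherapy, without withdrawing consent, keeps the remaining scheduled L* and photograph visits to week 12. This concerns data collection only.
3. Analyse every randomised patient with any post-baseline reading, with sides as randomised. Fit a repeated-measures model to the monthly within-patient tretinoin-minus-control differences in delta L*, with month as a factor and unstructured covariance, and report the week-12 mean difference. With complete data this equals the paired t-test estimate.
4. Keep the paired t-test on week-12 completers as a sensitivity analysis.

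Optionally, report VESTA response over all randomised patients, counting those without a photograph as non-responders on both sides. Such pairs are concordant, so the reported proportions change but the McNemar test does not; any selection in that test remains.

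**Cost.** A few sentences, and a standard model in R on readings already planned (visits after stopping may add some). The standard error may be slightly larger, and some off-treatment readings will dilute the on-treatment effect. The model corrects only for leaving that observed earlier readings explain, and it adds nothing for patients who leave before month 1. Continued measurement under item 2 therefore matters more than the model.
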